As a practicing oncologist within Stephenson Cancer Center, [name], Ph.D. is knowledgeable about the medical needs of the population that is being recruited for this study, and she regularly uses evidenced-based interventions to treat cancer. Her research and clinical experience complement [name] experience with research using mobile technology for health improvement. Additional study investigators include [name] (biostatistician) and [name] (basic and translational scientist) have agreed to assist with study recruitment and follow-up procedures.

D. Research Design and Methods

Study Design: A total of 500 treatment-seeking males and females will be asked to complete daily monitoring of symptoms and weekly monitoring of health risk factors weekly via smartphone app (Aim 1). Those who screen positive for COVID-19 will be triaged to emergency or non-emergency medical treatment. COVID-19 positive patients identified for non-emergent medical treatment will receive a study-supplied device to measure their oxygen level and heart rate and be instructed in the device's use. They will be prompted to enter vital signs data daily (such as body temperature, oxygen level, and heart rate) and questions from the app will change to assess the severity of COVID-19 related symptoms and inform changes in level of care, to emergency or non-emergency medical management as indicated by self-reporting. The proposed study will assess the impact of heightened symptom and vital sign monitoring on the early identification of severe manifestations of COVID-19 in this high-risk population (Aim 2). It is hypothesized that this will significantly improve COVID-19 related morbidity and mortality compared to the national and international rates currently reported in the literature. Figure 1 displays the participant flow through this 24-week study.

The SCC mHealth Shared Resource has created the versatile and reusable Insight™ mHealth Platform. Insight™ is HIPAA compliant and data are encrypted within the app. There will be 4 sources of data for the current study: 1) in-person data collected in a private room at the SCC

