predict study outcomes with less bias than traditional in-person assessments. EMA data will be used to identify and report COVID-19 symptoms to SCC medical staff, assess health risk factors, and collect other health related data that may be used to guide future intervention development with this population. All participants will download the assigned smartphone app to their personal smartphone or receive a smartphone at the baseline visit and will be asked to carry it with them at all times for 24 weeks. Participants will be trained to use the smartphone app for data collection purposes. Participants will be instructed to click the “call staff” button to speak with study research staff in the event that they have difficulty with the phone app. In addition, participants will be instructed that they can click the “Call Clinic Staff” button in the app to speak with medical professionals about their symptoms. In weeks 1-24, participants will be asked to complete one daily survey that will be automatically prompted and administered through an encrypted and secure smartphone app. All participants will be asked to self-initiate a survey (by clicking a button labeled “Report Symptoms” in the app) in the event that any new symptoms arise after the morning survey is completed. Participants will respond to survey questions by using the touch screen.

EMA types. The EMA methodology used in this study will be similar to what has been used in our previous studies, and by other researchers.[24, 25, 28, 30, 39-45] Each EMA will ask about current mood, medication use, perceived social support, pain, and symptoms consistent with COVID-19. This daily survey will take approximately 2 minutes to complete (see Table 1 and Appendix). Every Monday, participants will complete additional items focused on health risk factors, depression, anxiety, and medication use. The phone will ring and vibrate to cue these EMAs for 30 seconds. If the participant has not responded after 5 prompts, the EMA will be recorded as missed. Participants may also initiate a survey by clicking a Report Symptoms button in the app when COVID-19 symptoms arise later in the day (see Table 1 and Appendix). All EMAs will be date and time stamped for future analyses.

Table 1: Study Measures

MEASURE	ITE MS	FULL BATTERY ASSESSMENTS			Chart Revie w	EMA ASSESSMENTS
		Scree n	Bas e	24- W		
Descriptive Variables						
Screening Questionnaire	11	X				Sleep

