All participants will be prompted to complete EMAs once per day during the 24-week study time period. If a participant contracts COVID-19, they will click the “COVID-19 Positive” button in the app. This action will cause the app to ask a different set of questions focused on enhanced monitoring COVID-19 symptoms for the next 21 days. At the end of 21 days, the app will return to daily prompts of the pre-COVID-19 EMAs. At the conclusion of the 24-week EMA period, participants will gain access to a new button in the app that will initiate the 24-week follow-up assessment (see Appendix). Participants will receive a daily alert from the app to click the “Final Survey” button in the app to complete the end of study assessment. The 24-week phone interview (or RedCap interview if a medical condition prevents them from being able to speak for long periods of time) will be scheduled at the baseline visit and the date/time of the call will appear at the top of the app home screen. A maximum of five phone call/text attempts and one mailed letter will occur over two-week period, before data from phone interview (or RedCap interview if a medical condition prevents them from being able to speak for long periods of time) will be considered unattainable. Those participants who were loaned a mobile phone to use during the study will be mailed a stamped envelope to return the phone and charger, or will be approached by study staff to reclaim the mobile device during a routine follow-up visit in the SCC chemo infusion clinic. Upon receipt of the smartphone and charging equipment, all equipment will be sterilized with alcohol-based sanitizer in accordance with current practice guidelines put forth by the Centers for Disease Control at the time it is returned by the study subject.

EMA completion rates, participant dropout, and feedback on the participant satisfaction survey will be used to evaluate feasibility of this type of mobile intervention in this population.

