Qualitative interview data. A qualitative interview will be conducted at the end of the 24-week study period via a brief phone call (or RedCap if a medical condition prevents them from being able to speak for long periods of time). This interview will assess opinions about the app, ways the app could be improved for future patient monitoring, etc. The follow-up phone call will be recorded for transcription and analyzed using NVivo. Recordings will be transcribed by internal staff, Microsoft Transcribe, or by approved contractors with whom a Business Associates Agreement has been made. When using Microsoft Transcribe, all transcriptions will be reviewed by study staff. De-identified information will be shared with collaborators and colleagues at other NCI Designated Cancer Centers (see Aim 3).

Data from the electronic health record. Relevant data from the EHR will be extracted as needed to address any discrepancies or omissions surrounding specified study outcomes that have been collected through the smartphone EMA surveys. This supplemental information will be collected and stored in REDcap.

Private identifiable data (e.g., participant names, study assessment dates, and contact information) will be required for participant contact and thus will be collected in this study. Private identifiable data will be used to contact participants and will be saved in compliance with university storage of PHI (e.g., encryption). All printed private identifiable data will be stored in a locked filing cabinet in [name] research office when not in use and will be destroyed 12 months after data collection is completed.

Smartphone programming. The mHealth Shared Resource at the OUHSC and Stephenson Cancer Center (SCC) has developed the Insight™ mHealth Platform that empowers researchers to build, test, and launch technology-based assessment and intervention tools. The mHealth resource employs a program manager, four senior programmers, and two research technicians, who develop and maintain web and mobile applications and relational databases. Applications are developed using state-of-the-art cross-platform design tools. The Resource is located within the Oklahoma Tobacco Research Center (OTRC), where [name] office is located. [name] is the Scientific Director of the mHealth Shared Resource, which will provide the programming services for the proposed project.

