When participants provide a pattern of responses that are suggestive of heightened risk for COVID-19 (See algorithm in Appendix), they will receive a suggestion to contact SCC staff, and the app will send an encrypted email containing this information to [name] and other SCC staff with a request to contact the participant to assess symptoms (see Appendix) and whether urgent medical attention is indicated. Should urgent medical attention be warranted, the patient will be instructed to the clinical unit most appropriate to the symptoms they reported through the app algorithm or discussed with the clinical nursing or physician staff. Non-emergent patients who screen positive for COVID-19 will begin an enhanced symptom and vital sign monitoring period that will continue until the participant reports that they are no longer symptomatic and/or a medical professional informs them that they no longer need to self-quarantine, which is expected to be approximately 21 days. These patients will receive a pulse oximeter (provided by the study) and the app questions will change to include daily prompts requesting that the patient input morning vital signs (temperature, heart rate, blood oxygen levels (SpO2)) and answer questions specific to the severity of symptoms and/or emergence of new symptoms of COVID-19. If a patient is hospitalized, they can continue to complete the daily assessments if they are willing and able to do so. The app will also support check-ins with SCC staff and after-hours medical staff as needed after diagnosis of COVID-19 or until the patient has been medically released from self-quarantine. Once the participants have completed the enhanced symptom and vital sign monitoring portion of the study, the pulse oximeter will be returned to the research team at the time of their next scheduled appointment. These devices will then be sterilized with both alcohol-based sanitizing products as well as ultraviolet light exposure in accordance with practices endorsed by the Centers for Disease Control.

Participants will continue to use the app to complete a final 24-week follow-up survey and will be contacted by phone (or RedCap if a medical condition prevents them from being able to speak for long periods of time) to complete a brief qualitative interview 24 weeks after study enrollment. Relevant demographic, cancer-specific and COVID-19 related data will be extracted

from electronic health records at the conclusion of the study.

E. Chart Review

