In-person data. Participants will complete all assessments on their personal smartphone or a study provided smartphone using the Symptom Tracker (Insight™) mHealth platform app and/or the REDcap program. Participants will be instructed that they may elect to not answer questions that make them feel uncomfortable. All questionnaire data is automatically saved and password protected. To ensure that research staff are adequately trained in data collection, confidentiality, and the protection of human subjects, all project staff will complete extensive training focused on each of the following topics: 1) project rationale and objectives; 2) the informed consent process; and 3) general data collection procedures (e.g., computer data collection, privacy). They will also complete all confidentiality, conflict of interest, and HIPAA training programs as required by the University of Oklahoma Health Sciences Center.

EMA data. Participant responses to study questions will be encrypted and stored on the study/personal smartphone. Encrypted data will be automatically uploaded to our secure server each day. When/if the app determines that risk for COVID-19 infection is high, or COVID-19 symptoms are worsening (in those who contract the virus), an encrypted email will be sent from our secure server to clinical study staff that includes the participant name, date of birth and phone number. The following features are designed to ensure the security of this data: 1) the data stored on the smartphone device are in a SQLite database in a sandbox environment, where read/write operations are only available through the programming application (i.e., no file or output is readable to end users); 2) a 10-12 character password (only known to researchers) is required to authenticate the current user before data can be manually accessed; 3) the web browser application linking the investigator's computer to the database is on HTTPS protocol (SSL certificate with encryption) which will guarantee the data transfer from web browser to the backend database is well protected; and, 4) the backend database is hosted by Microsoft Azure and the University of Oklahoma Health Sciences Center. These steps will ensure the security of EMA data. Software will be downloaded onto each study phone so that study data can be remotely wiped if phones are lost or stolen.

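### The app drops enhanced COVID-19 monitoring on a fixed 21-day timer, although the protocol elsewhere continues it until symptoms end and/or medical release

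*Combined protocol and SAP*

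**What the plan says.** Two parts of section D (Research Design and Methods) set the length of enhanced monitoring.

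- **Measures, text after Table 1.** A participant who contracts COVID-19 presses the COVID-19 Positive button. "This action will cause the app to ask a different set of questions focused on enhanced monitoring COVID-19 symptoms for the next 21 days". Then: "At the end of 21 days, the app will return to daily prompts of the pre-COVID-19 EMAs".
- **Study application.** For non-emergent patients who screen positive, the enhanced symptom and vital-sign period "will continue until the participant reports that they are no longer symptomatic and/or a medical professional informs them" of release from quarantine. The length is given only as an expectation: "no longer need to self-quarantine, which is expected to be approximately 21 days". During this period the patient has a study oximeter, and the app asks each day for temperature, heart rate, SpO2 and the severity or emergence of symptoms. The oximeter goes back once this part of the study is complete.

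Study Design, also in section D, gives the purpose. The vital signs and severity answers are to "inform changes in level of care, to emergency or non-emergency medical management as indicated by self-reporting", and Aim 2 assesses the effect of this closer monitoring on early identification of severe disease.

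For the routine survey, EMA types says: "Each EMA will ask about current mood, medication use, perceived social support, pain, and symptoms consistent with COVID-19".

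**The concern.** The first rule is a timer and the second is a clinical criterion. They agree only when the criterion happens to be met at day 21. Programmers and clinic staff cannot follow both for a patient whose illness outlasts the timer.

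The direction that matters is prolonged illness. That patient still needs enhanced monitoring under Study application and still holds the oximeter, but an app built to Measures would no longer ask for its reading. These are the data meant to inform changes in level of care, and they are the closer monitoring that Aim 2 is meant to assess. They would stop by calendar, in a group that Background and Significance describes as high-risk, while the patient is still ill.

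**Working it through.** No arithmetic applies, because the question is which of two stopping rules governs. I set them side by side, then looked at what the routine survey keeps and what else in the text bears on the point.

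**1. The rules by patient status just after day 21**

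The criterion in Study application joins its two events with and/or, so both readings are shown.

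| Status after day 21 | Timer (Measures) | Criterion, either event ends it | Criterion, both events needed |
|---|---|---|---|
| Symptomatic, not released | enhanced set ended | continues | continues |
| Symptomatic, released | ended | ended | continues |
| Symptom-free, not released | ended | ended | continues |
| Symptom-free, released | ended | ended | ended |

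The first row conflicts whichever way and/or is read. The second and third rows conflict only if both events are required. So the core conflict does not depend on the ambiguity, but its extent does.

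**2. What stops and what stays when the app reverts**

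- *Stops:* daily prompts for temperature, heart rate and SpO2, and the questions on severity. Study application places these in the changed question set. Neither EMA types nor the EMA column of Table 1 lists vital signs in the routine survey.
- *Stays:* the daily COVID-19 symptom items (Table 1 gives 8), the alert for high-risk answers (Study application), the worsening alert in section K, under EMA data ("COVID-19 symptoms are worsening (in those who contract the virus), an encrypted email will be sent from our secure server to clinical study staff"), and the Report Symptoms and Call Clinic Staff buttons. Study application also provides as-needed check-ins with clinic and after-hours staff, with medical release as their end point. None of these is tied to the 21-day timer.

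**3. Is there a stated way to extend?**

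Smartphone training lists five app features: Call Staff, Call Clinic Staff, Report Symptoms, COVID-19 Positive and Update Contact Details. None is described as recording recovery or release, or as prolonging the enhanced set. The text neither limits the COVID-19 Positive button to one press nor says that a second press restarts the 21 days. It does not say which rule prevails.

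**4. Can the number affected be estimated?**

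It cannot. The protocol plans up to 500 participants but gives no expected COVID-19 incidence, symptom duration or time to release for them. The severe-infection and mortality figures in Background and Significance say nothing about how many patients are still ill after day 21.

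**The case against.** The best reply is that the two passages describe different things: Study application describes the clinical period, and Measures describes an app default set to its expected length of about 21 days. This explains where the number comes from. It does not remove the conflict, because an expected length is not a limit, and the patients who exceed it are the ones for whom a clinical criterion is needed.

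The second reply carries more weight. The text refers to an Appendix for survey content, app buttons and the alert algorithm, and that Appendix was not available. It may provide for an extension or a restart, so what the app actually does cannot be judged here. The main text would still need correcting, since as written it contradicts itself.

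The third reply, that much cover remains, stands in full. A reader might infer three stronger things that the documents do not support:

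- *That still-ill patients go unmonitored after day 21.* They do not. The loss is confined to the prompted vital-sign and severity entries.
- *That patients who recover early are harmed by staying on the enhanced set to day 21.* The text shows only extra prompting. Ending the set early on either event could be worse, because a patient released on, say, day 10 but still symptomatic would lose prompts that Measures now gives to day 21.
- *That the Aim 2 time-to-resolution curves or the Aim 1 feasibility measures are undermined.* COVID-19 symptoms are still asked about daily after the switch, and the protocol allows gaps to be filled: "Relevant data from the EHR will be extracted as needed to address any discrepancies or omissions surrounding specified study outcomes". Aim 1 does not depend on which stopping rule applies.

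**Conclusion.** The concern holds as a conflict between two operative rules, with a real but narrow consequence. If the app follows Measures, prompts for temperature, heart rate, SpO2 and severity end for a non-emergent patient who is still symptomatic and unreleased after day 21, and who under Study application should still receive them. Other cover continues, and the number of patients affected is unknown.

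This should be corrected. It is more than a slip of wording, because it decides when vital-sign monitoring of a sick patient stops, but it does not threaten the study's primary aim. Confidence is medium. The conclusion assumes that the app is programmed to the Measures text, that the Appendix has no extension or restart rule, and that the routine survey contains no vital signs, as its listed content indicates.

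**What to change.** Amend the Measures text so that 21 days is the minimum length of the enhanced set. After day 21 the set should extend automatically while the patient is still symptomatic or not yet medically released.

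To make this workable:

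- Add an entry, in the app or by staff, for symptom resolution and for medical release.
- Make day 21 a staff review. This also guards against prompts running on only because nobody entered a release.
- Replace the and/or in Study application with wording that matches: after the 21-day minimum, enhanced monitoring ends when symptoms have resolved and the patient has been released.
- If the Appendix already contains an extension rule, bring it into the main text and check that it agrees.

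**Cost.** A protocol correction, a small app change by the shared resource that already does the programming, and a brief staff check at day 21. Patients with prolonged illness get longer daily prompting and a longer oximeter loan. Study application already intends this for those both symptomatic and unreleased; for those meeting only one condition it depends on how and/or is read. Patients who recover early answer the enhanced set to day 21, as Measures already provides. No extra participants or visits are needed.

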The primary objective of this research is to use innovative mHealth technology to monitor symptoms in real-time and facilitate medical triage of high-risk patients. The current study will obtain data on the feasibility of an innovative mHealth application to track symptoms and automatically intervene upon reported high-risk symptoms among cancer patients who are receiving cytotoxic chemotherapy or immunotherapy treatments. This objective will be attained by pursuing the following specific aims:

1. Determine the feasibility, ease of use, and perceived utility of the Symptom Tracker (Insight™) mHealth app to monitor symptoms and health risk behaviors for up to 500 patients who are receiving chemotherapy to treat cancer.
 - a. On average, participants will complete >50% of all prompted daily phone based ecological momentary assessments (EMAs).

- b. Most participants will report that the app is easy to use, and provides useful information (assessed quantitatively and qualitatively during the 24-week phone based or RedCap follow-up interview).
2. Examine participant characteristics and outcomes of those who do and do not test positive for COVID-19 during the 24-week monitoring period.
 - a. Among those who undergo enhanced monitoring, we will use descriptive statistics to summarize the proportion of patients experiencing the following outcomes: manifestations of severe disease, treatment related toxicity, need for hospitalization, and SARS-CoV-2 related mortality.
 - b. We will also compare outcomes and tolerability of enhanced self-monitoring for severe infection and compare rates of disease related morbidity and mortality to baseline rates published in the literature.
 - c. We will use quantitative and qualitative methods to evaluate participant satisfaction with the app among those who test positive for COVID-19 and are asked to report vital signs each day.
3. Collaboratively document and share lessons learned regarding the impact of the COVID-19 pandemic on cancer care delivery via telemedicine and mHealth technology. We commit to a collegial collaboration with other cancer centers funded to study the use of telemedicine through the COVID-19 CCSG supplement mechanism.

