Study staff will conduct a chart review on OUHSC campus computers using OU Medicine's electronic medical record. Chart review will be conducted after completion of the EMA period. Initial evaluation, treatment plan, and follow-up notes will be searched for the following data points:

- a) Cancer Stage at Initial Presentation
- b) Type of Cancer – text field
- c) History of Previous Cancer Diagnosis
- d) Previous Cancer Treatment
- e) History of Previous Cancer Treatment with Surgery
- f) History of Previous Cancer Treatment with Chemotherapy
- g) History of Previous Cancer Treatment with Endocrine Therapy
- h) History of Previous Cancer Treatment with Radiation
- i) History of Previous Other Types of Cancer Treatment
- j) Receiving concurrent chemotherapy and radiation
- k) Body Mass Index at start of treatment
- l) Body Mass index at end of treatment
- m) Number of no-show and cancelled office visits
- n) Referral to Supportive Care
- o) Distance in miles from the participant's home to the SCC?
- p) Does the participant reside in a rural county?

All data collected during the chart review will be assigned to the corresponding participant ID number and entered into study electronic databases in accordance with the data and safety-monitoring plan outlined below. See Appendix for a full list of data that will be collected via chart review.

F. Biospecimens

No biospecimens will be collected as part of this study.

G. Banking/Repository/Database

No biospecimens will be banked for future use. All data will be stored and accessed on OUHSC devices/computers.

H. Inclusion / Exclusion Criteria

Individuals will be included in the study if they:

- 1) Demonstrate > 6th grade English literacy level (i.e., phone based EMAs require >6th grade literacy)
- 2) Present for care at the Stephenson Cancer Center at the University of Oklahoma Health Sciences Center
- 3) Are currently receiving cytotoxic chemotherapy or immunotherapy by intravenous infusion or by orally delivered medication
- 4) Are greater than or equal to 18 years of age
- 5) Are willing and able to complete surveys on their personal smartphone or a study provided smartphone
- 6) Are willing and able to provide informed consent

There are no early termination criteria; however, individuals can elect to stop participation in

mobile app monitoring at any time.

I. Gender/Minority/Pediatric Inclusion for Research

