This sample will consist of up to 500 male and female cancer patients. Individuals under the age of 18 (pediatric population) will be excluded from this study. Minorities will also be included, as this study seeks to adequately capture the diversity of patients receiving treatment at the SCC. There are no known additional risks for women or minorities.

J. Recruitment and Enrollment

Participants (N=500) will be recruited through the OU Medical Stephenson Cancer Center Infusion Clinic which is located at [name]. The SCC Infusion Clinic provides chemotherapy services for approximately 1200 patients per month. Based upon the treatment regimens provided, we anticipate that 250-300 cancer patients will be accrued to the trial every quarter. The clinic is staffed by oncologists, pharmacists, and advanced practice professionals. Patients will be given a verbal description of the study during a clinic visit, and those interested will be screened for study eligibility. Individuals who provide informed consent and meet the study inclusion criteria will complete the baseline assessment in the Infusion Clinic space. Participants will use study phones or personal smartphones to complete the baseline and follow-up assessment and phone-initiated and self-initiated surveys for the entire duration of the study. At the time of consent, patients will be provided with a copy of the informed consent to keep and will be encouraged to contact the investigators should they have further questions. The assessment questions are presented through the Insight™ mHealth platform. No incentive or cost reduction for care will be provided to the patient in order to minimize the risk of coercion. Several strategies will be utilized to retain study participants. Survey responses are automatically uploaded to the secure server every day; thus, study staff can closely monitor participant completion of daily surveys, and attempt to make contact with participants who do not complete them. Figure 1 displays the participant flow through the study.

K. Risks and Benefits

Participation in this study poses minimal risk to participants. Potential risks include consenting process and loss of confidentiality. Each of these risks are discussed below. The consent form will clearly describe the potential risks of this study. Thus, participants who feel uncomfortable with such assessments or intervention programs are not likely to agree to participate.

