Aim 1. We will examine the percentage of prompted daily surveys that are completed throughout the 24-week intervention period and the percentage of participants who report they are satisfied with monitoring and use of mHealth application at the end of the 24-week study period. We will compare participant characteristics (e.g., demographics, health behaviors) and outcomes between those who are satisfied with the app and monitoring versus those who are dissatisfied. We will observe via mHealth app patient health risk factors and readiness to change health risk behaviors in SCC cancer patients. We will compare participant characteristics using chi-square test or independent t-test, as appropriate. The follow-up phone call based qualitative interview (or RedCap interview if a medical condition prevents them from being able to speak for long periods of time) will access participant perceptions of each app feature and be recorded for transcription and analyzed using NVivo. Recordings will be transcribed by internal staff, Microsoft Transcribe, or by approved contractors with whom a Business Associates Agreement has been made. When using Microsoft Transcribe, all transcriptions will be reviewed by study staff. This information will be used to improve this type of symptom monitoring apps in future studies and interventions.

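### Uptake is not among the stated feasibility measures, so a favourable result on the primary aim could coexist with low uptake and the study could not show it

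*Combined protocol and SAP*

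**What the plan says.** The Abstract names feasibility, ease of use and perceived utility as the primary aim. Section D, in the text following Table 1, gives the basis for judging it: "EMA completion rates, participant dropout, and feedback on the participant satisfaction survey will be used to evaluate feasibility". That sentence goes on to apply the judgement to the population under study, not only to those who enrol.

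The other statements of the aim use enrolled people as the denominator. Aim 1a in section A sets a threshold of more than 50% of prompted surveys completed, averaged over participants. Aim 1b asks that most participants find the app easy and useful. Section M, Aim 1, analyses "the percentage of prompted daily surveys that are completed throughout the 24-week intervention period" and the percentage of participants who are satisfied.

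Entry to that denominator passes two filters. Section J describes the study verbally to patients at a clinic visit, after which "those interested will be screened for study eligibility". Section H, criterion 5, requires that they "Are willing and able to complete surveys on their personal smartphone or a study provided smartphone".

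On volume, section J says "The SCC Infusion Clinic provides chemotherapy services for approximately 1200 patients per month" and "we anticipate that 250-300 cancer patients will be accrued to the trial every quarter", with total enrolment of 500 (elsewhere up to 500). No section gives a consent rate, a refusal rate or a plan to count patients approached.

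**The concern.** One obvious way for a daily app to fail in a chemotherapy clinic is that patients decline it. The task here is a daily survey for 24 weeks without compensation, so refusal is plausible. Under the stated measures refusal cannot affect the conclusion: a patient who hears the description and declines contributes to none of completion, dropout or satisfaction.

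Selection by consent affects every study, but it matters more here because feasibility is itself the primary question. The results are also meant to inform fully powered randomised trials (Abstract) and an R01 application (section A). Planning accrual for those needs a consent rate as well as a completion rate. The 82-87% completion from the team's earlier work, cited in section D under smartphone training, is likewise among participants and says nothing about uptake. If approaches are not logged as they happen, refusals cannot be reliably reconstructed afterwards.

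**Working it through.** The plan contains no uptake figure, so there is none to reproduce. The check is what the planned data could and could not distinguish.

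**Inputs from the documents**
- Enrolment: 500 (section J).
- Accrual: 250-300 per quarter (section J).
- Clinic volume: about 1200 patients per month (section J).
- Completion target: above 50% on average among participants (Aim 1a).

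**Inputs assumed, because the documents give none**
- Patients approached and not known to be ineligible: 600, 1000 or 2500.
- Completion in consenters: 70%.
- Completion decliners would have had: 20% to 40%.

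**Step 1. Can accrual over volume stand in for uptake?** The number of distinct clinic patients per quarter is not given. It lies between 1200 (the same people every month) and 3 × 1200 = 3600 (all new).
- Per quarter: 250/3600 = 6.9% up to 300/1200 = 25.0%.
- Recruiting 500 takes 500/300 = 1.7 to 500/250 = 2.0 quarters. Against a static pool of 1200, the share over full accrual could reach 500/1200 = 41.7%.

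These ratios describe a capped enrolment against everyone attending the clinic, including people never approached and people who are ineligible. They are not an acceptance rate.

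**Step 2. Uptake compatible with the same 500 enrolled.** Uptake u = 500 / number approached. Completion among all approached = u × 70% + (1 − u) × d, where d is what decliners would have completed.

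| Approached (assumed) | Uptake u | Completion, d = 20% | Completion, d = 40% | Study reports |
|---|---|---|---|---|
| 600 | 83% | 58.3 + 3.3 = 61.7% | 58.3 + 6.7 = 65.0% | 70% |
| 1000 | 50% | 35 + 10 = 45% | 35 + 20 = 55% | 70% |
| 2500 | 20% | 14 + 16 = 30% | 14 + 32 = 46% | 70% |

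**Step 3. Where the answer crosses 50%.** Setting the expression equal to 50% gives u = (50 − d)/(70 − d).
- d = 20%: 30/50 = 60% uptake, or 500/0.60 = 833 approached.
- d = 40%: 10/30 = 33% uptake, or 500/0.333 = 1500 approached.

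Under these assumptions, whether completion among all approached exceeds the target depends on how many were approached, which no available text plans to record.

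**Step 4. Precision of uptake if it were recorded.** At 500 of 1000 the 95% half-width is 1.96 × √(0.5 × 0.5/1000) = 0.031, about ±3 percentage points.

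**The case against.** Several points on the other side have force.

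- **Aim 1a already speaks of participants.** Only the section D sentence reaches further. Later randomised trials would also enrol consenters, so completion among consenters is a relevant planning figure. This stands: the absence of uptake does not invalidate the 50% criterion for those who enrol.
- **A log may exist where it cannot be checked.** Section J is silent on whether approaches are recorded, and Figure 1 (participant flow) and the Appendix were not available. This also stands. The point can say only that no available text plans such a count.
- **Screening data are partly there.** Section D places the study screener in REDCap, and Table 1 lists an 11-item screening questionnaire and a literacy test. Ineligibility among those screened is therefore probably captured. The gap is mainly people who decline before screening.
- **Access is supported.** Section D lends phones to patients without a suitable phone or data plan and provides training. Loaned phones reduce the device barrier, but not unwillingness or illness burden.

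A reader might also infer from section J that uptake is only 7-25%, and so that most patients would not take up the app. The documents do not support this. The ratio is one quarter's accrual over clinic volume. The same 500 could be 83% or 20% of those approached, and the share over full accrual could reach 41.7%. Nor does it follow that completion across the clinic must fall below 50%. At 83% uptake the assumed figures give 62-65%. Even treating 500/1200 as uptake, with decliners at 40%, gives 0.417 × 70 + 0.583 × 40 = 52.5%.

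**Conclusion.** The concern holds in a limited form. Uptake is not a stated feasibility measure, and no available text plans to count patients approached or declining. The section D conclusion is nonetheless worded for the patient population. A favourable result could therefore coexist with low uptake, and the study could not show it.

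The true size is unknown, since the documents give no number approached. In the illustration, completion among all approached ranges from 30% to 65% while the reported figure stays at 70%. That range rests wholly on the assumed numbers approached and the assumed completion rates. It shows what the plan cannot distinguish and does not predict low uptake. Completion among consenting patients remains a valid and useful result. This is an inexpensive improvement worth making, and not a flaw that undermines the study.

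**What to change.** - **Section J:** keep anonymous counts of patients given the verbal description, declining (with main reason), screened, ineligible by criterion, and consented. Hold them alongside the existing REDCap screener. If Figure 1 or the Appendix already provides for this, cite it.
- **Sections D and M (Aim 1):** add uptake as a feasibility measure, defined as consented divided by approached and not known to be ineligible. Report it with a 95% confidence interval beside survey completion.
- **Section D:** limit the feasibility conclusion to consenting patients unless uptake supports a wider claim. Aim 1a needs no rewording.

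The cost is a short log entry per patient approached, which is some added work before consent for whoever gives the description (section J does not say who), and one extra table. Sample size, visits and patient procedures are unchanged. The downside is that the feasibility headline may be less favourable.
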